Honest Open and Proud (HOP) programme, which is a peer-led approach, provides an opportunity for patients to discuss mental health stigma and explore their disclosure decisions with peers has shown promise. This has recently been modified and changed to Let's Talk through review of the workbook, manual and through Public and Patient Involvement. Three pilot randomised controlled trials (RCTs)³⁻⁵ have looked at the efficacy of Let's Talk but none of these have been conducted in the UK or with those experiencing psychosis.

2. Study Aims and Objectives

The principal objective is to evaluate the feasibility and acceptability of conducting a RCT of the 'Let's Talk' per-delivered intervention with people who experience psychosis.

The specific objectives of the trial are to assess:

 The proportion of eligible people clinicians are willing to refer, the proportion of eligible people willing to participate, the proportion of participants who engage with the intervention

- 2. The proportion of participants who select in-person vs. remote delivery of the Let's Talk peer-delivered intervention.
- 3. The drop-out rate.
- 4. The characteristics of trial participants to refine selection criteria.
- 5. The appropriateness and integrity of Let's Talk workbook and manual.
- 6. The feasibility and acceptability of the intervention to participants.
- 7. The randomisation procedures.
- 8. The relevance (to participants) and validity of the measures to assess effectiveness, service use, health status, safety and acceptability in a subsequent definitive trial.

3. General Study Design

A feasibility trial of a pragmatic, parallel group patient randomised superiority trial comparing Let's Talk plus treatment as usual (TAU) or TAU alone.

4. Interventions to be evaluated

Let's Talk plus treatment as usual: Let's Talk is an adaptation of the HOP program. HOP comprises of a workbook and manual and is delivered in a group format by one or more facilitators trained in the manual and at least one facilitator that has lived with experience of a mental heal problem³⁻⁵. Let's Talk has been adapted to ensure localisation to the UK context and delivery in a one-to-one setting by a peer support worker with up to 10 weeks of the programme.

Treatment as usual: this includes early intervention in psychosis and secondary care adult mental health services.

5. Randomisation, Allocation and Blinding

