All participants who agree to enter the study will be logged with the central trial office and given a unique Study Number. Randomisation will utilise the existing proven remote automated computer randomisation application in the central trial office in the Centre for Healthcare Randomised Trials (CHaRT, a fully registered UK CRN clinical trials unit) in the Health Services Research Unit (HSRU), University of Aberdeen. Randomisation will be computer-allocated using randomised-permuted blocks of random size. The unit of randomisation will be the participant and on a 1:1 ratio stratified by centre and delivery mode (in person or remote). No blinding of the treatment allocation will be done.

6. Outcome Measures

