6.2. Outcome measures

Outcomes measures will be collected to determine their suitability for use in a definitive trial and identify a suitable primary outcome for a definitive trial, rather than to draw conclusions about efficacy of treatments. In addition to demographics, we will collect the following outcomes:

- 1. The Semi-structured Interview Measure for Stigma in Psychosis (SIMS)⁶;
- 2. Disclosure Stress Scale (DDS)⁵;
- 3. Stigma Stress Scale⁷;
- 4. The Process of Recovery Questionnaire (QPR)⁸;
- 5. The Calgary Depression Rating Scale for Schizophrenia (CDS)⁹;
- 6. Social Interaction Anxiety Scale (SIAS)¹⁰;
- 7. Manchester Short Assessment of Quality of Life Scale (MANSA)¹¹;
- 8. Rogers Empowerment Scale (RES)¹²;
- 9. Economic patient questionnaire¹³;
- 10. EuroQol Group's 5-dimension health status questionnaire 5 level (EQ5D-5L)¹⁴.

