6.3. Mediators

We will collect data on the below potential mediators of change to determine feasibility of collecting these measures in a definitive trial to answer important hypotheses about mediators:

- 1. Internalised Shame Scale (ISS)¹⁵;
- 2. Self-Esteem Rating Scale (SERS)¹⁶.

7. Timing of Outcome Measurements

Outcome Measure	Baseline	End of treatment (2.5	6 months ¹
		months ¹)	
SIMS	~	√	√
DDS	~	\checkmark	\checkmark
Stigma Stress Scale	~	\checkmark	\checkmark
QPR	~	\checkmark	\checkmark
CDS	✓	\checkmark	\checkmark
SIAS	✓	\checkmark	\checkmark
MANSA	✓	\checkmark	\checkmark
RES	~	\checkmark	\checkmark
Economic patient	✓	\checkmark	\checkmark
questionnaire			
EQ5D-5L	✓	✓	\checkmark
ISS	✓	✓	\checkmark
SERS	\checkmark	\checkmark	\checkmark

¹ post-randomisation

8. Progression criteria

The progression criteria to a definitive trial are:

- Recruitment rate within ≥80% (green); 79-60% (amber); <60% (red) of planned target.
- Retention of participants within the study with ≥ 80% (green); 79-60% (amber);
 <60% (red) of data for the Semi-structured Interview Measure of Stigma (SIMS⁶)

or Stigma Stress Scale⁷, which are the proposed primary outcomes for a definitive trial.

 ≥ 80% (green); 79-60% (amber); <60% (red) of those allocated to Let's Talk receiving at least two sessions.

9. Adverse Events

A serious adverse event (SAE) is:

- All death;
- Suicide attempts;
- Serious violent incidents;
- Any other life-threatening incident;
- Admissions to a psychiatric hospital;
- Formal complaints about the study.

Please see the Study Protocol for more details on AEs. The number SAEs and the proportion of participants with an event will be presented. These will be tabulated and not analysed and will be summarised by Intention-to-Treat (ITT) and as treated.

10. Sample Size and Power Calculation

Outcome data on 60 participants is needed to estimate the standard deviation (SD) required for a sample size calculation for a definitive trial. We have used the advice from Whitehead et al¹⁷ to plan ahead for a trial with 90% power and potential small-to-moderate effect size (standardised effect size ranging from 0.2 to 0.4). To allow 20% attrition, we will recruit 75 participants. A pilot study of this size will allow to test procedures and gather information on other trial design and process elements that are listed in the objectives section.

11. Statistical Methods

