11.1. General Methods

All the main analyses will be based on the ITT principle. Final analysis will take place after full recruitment and follow-up. The results of the trial will be presented following the Consolidated Standards of Reporting Trials (CONSORT) 2010 Statement: extension to randomised pilot and feasibility trials¹⁸. As this is a feasibility trial, the main focus will be to summarise baseline and follow-up data using the appropriate descriptive statistics and graphical summaries. However, we will also look at treatment effects which will be presented with 95% confidence intervals (CIs). There will be no adjustment to secondary outcomes for multiple testing. All eligible participants will be included in the analysis and who provided consent. Any post-randomisation exclusions will be removed and reported as such and agreed with the PMG. Model assumptions will be checked and dealt with appropriately. See Appendix (section 16) for how patient reported outcome measures (PROMS) are derived along with Stata code for the analysis of the outcomes.

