11.4. Outcome measures

To inform a definitive trial analysis, the proposed outcomes (see section 6.2, apart from economic patient questionnaire) will be analysed using repeated-measures mixed-effects regression model correcting for baseline score and time as a categorical fixed effect and centre, mode of delivery, and participant as a random effect. The repeated measures will be assessed at 2.5 and 6 months post-randomisation with treatment effects estimates from a time-by-treatment interactions at each time point. Data missing at baseline will be reported as such. For the analysis, missing baseline data will be imputed using the centre-specific mean of that variable. Economic data collected by the economic patient questionnaire will be summarised using appropriate descriptive statistics.

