16.2. Stata code

Table 16.2 provides sample Stata code for the analysis, each outcome (see section 6.2) will be analysed the same therefore the code below will be used for all outcomes.

Outcome	Stata code
SIMS	<pre>mixed sims sims_b i.letstalk##i.TimePoint CentreNo: deleverymode: StudyNo: c sims sq is continuous sims _b is continuous baseline score letstalk binary (coded 0 for TAU and 1 Let's Talk plus TAU TimePoint is a categorical variable corresponds to the follow-up time points (coded 2 = 2.5 months, 6 = 6 months) CentreNo categorical (corresponds to each recruiting centre) deleverymode 0 = in person; 1 = remote StudyNo is a unique participant identifier Treatment effect for 2.5 months lincomest _b[1. letstalk] Treatment effect for 6 months lincomest _b[1. letstalk] + _b[1. letstalk #6.TimePoint]</pre>

Table 16.2 Stata code

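### The outcome model has no peer support worker term and no table reports caseload; if the worker ICC is above 0, the 95% CIs are too narrow, modestly so in most scenarios

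*SAP*

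**What the plan says.** - **Delivery.** Section 4 describes "delivery in a one-to-one setting by a peer support worker with up to 10 weeks of the programme". The number of workers and participants per worker are not given.
- **Comparator.** Section 3 describes a trial "comparing Let's Talk plus treatment as usual (TAU) or TAU alone", so no control participant has a Let's Talk worker.
- **Randomisation.** Section 5: "The unit of randomisation will be the participant and on a 1:1 ratio stratified by centre and delivery mode". Both stratifiers apply to both arms.
- **Model.** Section 11.4 has baseline score, time and time-by-treatment terms, with "centre, mode of delivery, and participant as a random effect". The sample code in 16.2, meant for all outcomes, has the levels "CentreNo: deleverymode: StudyNo". Neither has a worker term.
- **Reporting.** Section 11.1 presents treatment effects with 95% CIs, and dummy Table 13.4 adds a p-value column. Table 13.1 covers attendance and fidelity but not workers or caseloads.
- **Purpose.** Section 6.2 says outcomes are collected to judge their suitability and choose a primary outcome, "rather than to draw conclusions about efficacy of treatments". Section 10 sizes the trial to estimate the SD "required for a sample size calculation for a definitive trial". Section 11.4 says the model is there to inform the definitive trial's analysis.

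**The concern.** The design is partially nested: a limited number of workers share the Let's Talk participants, while control participants are not grouped in this way. In a relational, peer-delivered intervention, outcomes under the same worker may be correlated. The fitted model puts any such worker effect into the participant-level variance and treats it as independent from one participant to the next. The SE of the treatment difference is then too small.

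Two things are at stake. The reported intervals and p-values may look more precise than they are. The trial may also finish without reporting the caseload that a definitive trial would need to choose a design effect.

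**Working it through.** **Inputs from the SAP.** 60 participants with outcome data, 20% attrition and 75 recruited (section 10); 1:1 allocation (section 5); 95% CIs (section 11.1); 90% power and standardised effect 0.2 to 0.4 for the definitive trial (section 10).

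**Assumptions.** Worker ICC 0.01 to 0.10; 2, 4, 6 or 8 workers with equal caseloads; equal total variance in the two arms; two-sided alpha 0.05.

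**1. The plan's own figure.** 60 / (1 − 0.20) = 75, an exact match. Clustering plays no part in it.

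**2. Arm size.** The model uses participants with outcome data: 60 / 2 = 30 per arm, so with k workers the caseload is m = 30/k.

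**3. Formulas.** The Let's Talk arm has design effect DE = 1 + (m − 1) × ICC and the control arm has 1. The true variance of the difference is proportional to 1 + DE, where the model assumes 2. Hence:
- true SE / model SE = sqrt((1 + DE)/2)
- actual coverage = 2Φ(1.96 / ratio) − 1

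**4. Results.**

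| Workers | m | ICC | DE | SE ratio | Coverage |
|---|---|---|---|---|---|
| 2 | 15 | 0.01 | 1.14 | 1.034 | 94.2% |
| 2 | 15 | 0.05 | 1.70 | 1.162 | 90.8% |
| 2 | 15 | 0.10 | 2.40 | 1.304 | 86.7% |
| 4 | 7.5 | 0.01 | 1.065 | 1.016 | 94.6% |
| 4 | 7.5 | 0.05 | 1.325 | 1.078 | 93.1% |
| 4 | 7.5 | 0.10 | 1.65 | 1.151 | 91.1% |
| 6 | 5 | 0.01 | 1.04 | 1.010 | 94.8% |
| 6 | 5 | 0.05 | 1.20 | 1.049 | 93.8% |
| 6 | 5 | 0.10 | 1.40 | 1.095 | 92.6% |
| 8 | 3.75 | 0.05 | 1.1375 | 1.034 | 94.2% |

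At ICC 0 the ratio is 1 and nothing changes.

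**5. Does the centre term absorb it?** No. A simplified simulation used 60 participants, two centres, workers nested in centre, one time point and centre as a fixed effect. With 2 workers (one per centre), coverage was 94.9% at ICC 0, 90.3% at 0.05 and 85.4% at 0.10. With 6 workers it was 94.3%, 92.9% and 92.1%. A term common to both arms cannot represent an effect present in only one.

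**6. Is the SD biased?** Hardly. Within the arm, E[s²] = σ²[1 − ICC(m − 1)/(N − 1)]. With N = 30 and ICC 0.05:
- 4 workers: 0.05 × 6.5/29 = 1.1% low in variance, about 0.6% in SD.
- 2 workers: 0.05 × 14/29 = 2.4% low in variance, about 1.2% in SD.

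**7. What a design effect could mean for the definitive trial (illustration).** Without clustering, 90% power needs 526 per arm at effect 0.2 or 132 at 0.4. With m = 15 and ICC 0.05 the multiplier is (1 + 1.70)/2 = 1.35, giving 711 or 179 per arm. Uninflated, power would be about 80%. At ICC 0.01 the figures are 563 or 142 per arm, and uninflated power is about 88%.

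**The case against.** The other side has a good case on consequences.

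- **The ICC and worker count are unknown.** A reader might infer that the intervals are too narrow as a matter of fact. The SAP does not support that: it holds only for a positive ICC, and at ICC 0.01 or with many workers the effect is negligible. This stands.
- **The definitive trial.** A reader might infer that it will be sized without a design effect, or from a faulty SD. Section 10 says only that this trial supplies the SD; it neither sets nor excludes a design effect, and step 6 shows the SD is nearly unbiased. Undersizing would need a later decision that this SAP does not govern. This stands.
- **No decision depends on the intervals.** Efficacy conclusions are disclaimed, the main focus is descriptive, and all three progression criteria in section 8 are proportions. This stands and limits the priority.
- **A few workers cannot yield a usable variance estimate.** True, and it is why the fix keeps the main model and uses assumed ICCs. Any reader could apply the same multiplier after publication, but only if the caseload is reported.
- **Worker numbers may be in the protocol.** They may be, and their absence from the SAP's description of the intervention is no fault. The model and the results tables are the SAP's own business, however, and neither takes account of the worker. The general undertaking in 11.1 to check model assumptions does not name this one.

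**Conclusion.** The omission is real in both text and code, it affects one arm only, and the centre and mode terms do not stand in for it. If the worker ICC exceeds 0, the reported 95% CIs are too narrow and the p-values too small. Across 2 to 6 workers and ICC 0.01 to 0.10, the correct SE is 1% to 30% larger than the model's. These sizes rest on the assumed ICCs and worker counts, equal caseloads and 30 analysed per arm.

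For the definitive trial, the fault is only that no caseload is reported to inform a design effect. This is a cheap improvement of modest priority.

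**What to change.** 1. Record the peer support worker for each Let's Talk participant. Add to Table 13.1 the number of workers and participants per worker (median, range).
2. Keep the main model in 11.4. For the SIMS and Stigma Stress Scale differences, add a sensitivity 95% CI with the SE multiplied by sqrt((1 + DE)/2), DE = 1 + (m − 1) × ICC, for ICC 0.01, 0.05 and 0.10. Here m is the observed caseload among analysed participants.
3. State in 11.4 that the main CIs assume no clustering by worker.
4. State that the definitive sample size will consider a design effect over this ICC range.

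The cost is a few lines of SAP text, one identifier per Let's Talk participant (session records may already hold it, but the SAP does not say so) and a little more analysis. The downside is wider sensitivity intervals beside the main ones.

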11.5. Mediators

The mediators, defined in section 6.3 will be summarised using appropriate descriptive statistics. Mediation analysis aims to decompose a total effect (ITT effect) into an indirect effect, which measures how much of the effect acts through an intermediate variable, and a residual direct effect which measures how much of the effect does not act through the mediator. However, formal analysis will be considered.

11.6. Missing Data

11.7. Missing Outcome Data

As this is a feasibility study there will be no formal analysis to account for missing data.

11.8. Statistical software

All analysis will be carried out in Stata¹⁹ (or the current version available).

12. COVID-19

The effect of COVD-19 defined as 11th March 2020 ²⁰ or after will be explored. In the first instance, periods before, during and after COVID-19 will be summarised using appropriate descriptive statistics and graphical summaries. If need be, formal analysis will be carried out to explore the effect of COVID-19.

13. Dummy Tables

Table 13.1 Feasibility outcomes

	Let's Talk + TAU N=	TAU N=	Total N=
Referral rates – n (%)	NA	NA	
Recruitment – n (%)	NA	NA	
Attendance at the Let's Talk sessions		NA	
(number of sessions) ¹ – n (%)			
≥ 80%			
60 -79%			
<60%			
Fidelity to the Let's Talk manual and		NA	
principles of peer support and the most used			
Let's Talk strategies – n (%)			
Fidelity to peer principles			

Most used strategies (all sessions	
and by session)	
Fidelity to the Let's Talk strategies – n (%)	NA
Fidelity to peer principles	
Most used strategies (all sessions	
and by session)	
Follow-up/questionnaire response rates ² – n	
(%)	
SIMS Total	
Stigma stress	
¹ of those receiving at least two sessions. This will also be summarised by delivery mothe primary end point but 6 months will also be reported.	ode. ² 2.5 months is

Table 13.2 Recruitment by centre

Centre	Let's Talk + TAU N=	TAU N=
Greater Manchester Mental health NHS foundation trust		
North East London NHS Foundation Trust		

Table 13.3 Baseline characteristics

	Let's Talk + TAU N=	TAU N=
Age – mean (SD); n		
Gender – n (%)		
Female		
Male		
Nonbinary		
Prefer not to say		
Transgender male		
Transgender Female		
Other		
Highest level of education – n (%)		
Primary		
Secondary		
Further		
Higher		
Employment status – n (%)		
Full-time		
Part-time		
Voluntary		
College student		
University student		
Carer		

Unemployed Marital status – n (%) Single Married Divorced Separated Windowed Cohabiting Civil partnership[Living arrangements – n (%) Parents Partner Alone Friends Carer Other Ethnicity – n (%) White Mixed/ Multiple ethnic groups Asian/ Asian British Black/ African/ Caribbean/ Black British Chinese Arab Other Religion/belief – n (%) Atheism **Buddhism** Christianity Islam Jainism Sikhism Judaism Hinduism Other Disclosure stress scale - mean (SD); n The process of recovery questionnaire - mean (SD); n The Calgary depression scale - mean (SD); n Manchester Short Assessment - mean (SD); n EQ-5D-5L - mean (SD); n Social Interaction Anxiety Scale - mean (SD); Rogers Empowerment Scale - mean (SD); n The Semi-structured Interview Measure for Stigma in Psychosis - mean (SD); n Stigma Stress Scale - mean (SD); n Self esteem rating scale - mean (SD); n Internalised Shame Scale - mean (SD); n SD standard deviation

Table 13.4 Outcome measures

	Let's Talk	TAU	MD	95%	p-
	+ TAU N=	N=		CI	value
Disclosure distress scale – mean (SD);					
n					
Baseline					
2.5 months					
6 months					
The process of recovery questionnaire					
– mean (SD); n					
Baseline					
2.5 months					
6 months					
The Calgary depression scale – mean					
(SD); n					
Baseline					
2.5 months					
6 months					
Manchester Short Assessment – mean					
(SD); n					
Baseline					
2.5 months					
6 months					
EQ-5D-5L – mean (SD); n					
Baseline					
2.5 months					
6 months					
Social Interaction Anxiety Scale –					
mean (SD);					
Baseline					
2.5 months					
6 months					
Rogers Empowerment Scale – mean					
(SD); n					
Baseline					
2.5 months					
6 months					
The Semi-structured Interview					
Measure for Stigma in Psychosis –					
mean (SD); n					
Baseline					
2.5 months					
6 months					
Stigma Stress Scale – mean (SD); n					
Baseline					
2.5 months					
6 months					

SD standard deviation; MD mean difference; CI confidence interval

Table 13.5 Mediators

	Let's Talk	TAU N=
	+ TAU N=	
Self esteem rating scale – mean (SD); n		
Internalised Shame Scale – mean (SD); n		
Baseline		
2.5 months		
6 months		
SD standard deviation		

SD standard deviation

Table 13.6 Serious adverse events

	Let's Talk + TAU N=	TAU N=
Number of serious adverse events – n (%)		
Number of participants with a serious adverse event - n		
Details - n		
Death		
Suicide attempts		
Serious violent incidents		
Any other life-threatening incident		
Admissions to a psychiatric hospital		
Formal complaints about the study		

Table 13.7 Economics – 2.5 and 6 months

	Let's Talk + TAU N=	TAU N=
Planned hospital overnight stays		
Yes		
No		
Don't know		
Department stayed in		
Etc.		
Attended hospital outpatient appointments for less		
than 4 hours		
Yes		
No		
Don't know		
Department or specialty		
Etc.		
Attended hospital outpatient appointments for		
more than 4 hours (but not overnight)		
Yes		
No		
Don't know		
Department or specialty		

Etc. Attended Accident and Emergency Yes No Don't know Attended any primary and community based health services GP (at surgery/practice) Yes No Don't know GP at home Yes No Don't know Practice nurse (at surgery) Yes No Don't know Practice nurse at home Yes No Don't know Other physical care services Yes No Don't know Walk-in-centre Yes No Don't know Other Yes No Don't know Mental health services Yes No Don't know Counsellor or mental health worker Yes No Don't know Other social support services Yes No Don't know Other health or social care or support services Yes

No	
Don't	know

Values are numbers (percent)

14. Dummy Figures

15. References

1. Goffman E. *Stigma: Notes on the management of spoiled identity.* Touchstone; 2009. https://books.google.co.uk/books?id=zuMFXuTMAqAC.

https://www.cambridge.org/core/article/efficacy-of-coming-out-proud-to-reduce-stigmasimpact-among-people-with-mental-illness-pilot-randomised-controlled-

trial/625C49C74B579A3A98CE1D7BC32D4EA8. Accessed 2022/07/04. doi:

10.1192/bjp.bp.113.135772.

16.1. Derived Patient reported Outcome Measures (PROMs)

The PROMs are listed in section 6.2 and section 6.3. Codes developed in-house will be checked and validated by an independent statistician using dummy data. Table 16.1 describes how each score will be calculated.

PROMs	Calculation
The Semi-structured Interview Measure for Stigma in Psychosis	SIMS comprises of 11 items but only ten are included in the total score (understanding stigma is not included). Each item is scored between 0 (no impact/experience of stigma) to 4, (severe impact/experience of sigma). A total score is calculated by adding up all 10 items and ranges from 0 to 40. Currently there is no recommendations on when at least one item is missing for a participant. Therefore, if this occurs a total score will not be calculated for this participant. Positive impacts are reverse scored.
Disclosure Stress Scale	1 item question, ranging from 1 to 7. ⁵
Stigma Stress Scale	An eight-item measure that assesses Cognitive appraisal of stigma as a stressor. Items are rating on a 1-7 point Likert Scale with 1= strongly disagree and 7 = strongly agree. Four items assessed the primary appraisal of stigma as harmful (items 1-4) and four items the secondary appraisal of perceived resources to cope with stigma (items 5-8). A single stress appraisal score is computed by subtracting perceived resources to cope from perceived harmfulness. Currently there is no recommendations on when at least one item is missing for a participant. Therefore, if this occurs a total score will not be calculated for this participant.
The Process of Recovery Questionnaire	15 item questionnaire. Scoring is from 1 to 5 with 1 = Disagree strongly and 5 = Agree Strongly. a total score is created by adding up all 15 items. ⁸ Currently

Table 16.1 Calculation of PROMs score

	there is no recommendations on when at least one item is missing for a participant. Therefore, if this occurs a total score will not be calculated for this participant.
The Calgary Depression Rating Scale for Schizophrenia	9 item questionnaire, score 0 for absent up to 3 for severe. A total score is calculated but adding up all items and ranges from 0 to 27. ^{21,22} Currently there is no recommendations on when at least one item is missing for a participant. Therefore, if this occurs a total score will not be calculated for this participant. Currently there is no recommendations on when at least one item is missing for a participant. Therefore, if this occurs a total score will not be calculated for this participant.
Social Interaction Anxiety Scale	Scoring is from 0 to 4 with 0 = not at all characteristic or true of me and 4 = extremely characteristic or true of me. A total score is created from the 20 questions with question 5, 9 and 11 reversed. Currently there is no recommendations on when at least one item is missing for a participant. Therefore, if this occurs a total score will not be calculated for this participant.
Manchester Short Assessment of Quality of Life Scale	Satisfaction scoring across life domains is on a 1-7 Likert Scale with 1 = terrible and 7 = delighted MANSA Total Satisfaction = Q1 + Q2 + Q10a or Q10b* + Q14 + Q18 + Q23 + Q24 + Q28 + Q32 + Q36a or Q36b + Q40 + Q43 * item 10 assess satisfaction with working arrangements. Item 10a to be completed if working and item 10b to be completed if the person is not working. ** item 36 assesses satisfaction with living arrangements item 36a to be completed if the person lives with someone and item 36b to be completed if living alone. Currently there is no recommendations on when at least one item is missing for a participant. Therefore, if this occurs a total score will not be calculated for this participant

Rogers Empowerment Scale	28 item questionnaire, scored between 1 (strongly agree) to 4 strongly disagree. A total score is the sum of all items. ¹² Currently there is no recommendations on when at least one item is missing for a participant. Therefore, if this occurs a total score will not be calculated for this participant. Currently there is no recommendations on when at least one item is missing for a participant. Therefore, if this occurs a total score will not be calculated for this participant.
EQ-5D-5L	EQ-5D-5L is calculated using value sets available at Cross-walk – EQ-5D (eurogol.org)
Internalised Shame Scale	Scoring is from 1 to 5 with 1 = never and 5 = almost always. Questions 4, 9, 14, 18, 21 and 28 are reverse scored. Total score is 30 questions added together. Currently there is no recommendations on when at least one item is missing for a participant. Therefore, if this occurs a total score will not be calculated for this participant.
Self-Esteem Rating Scale	Scoring is from 1 to 7 with 1 = never and 7 = always. There are 10 positive and 10 negative items with 10 being scored positively and the other 10 are reversed scored (ones marked with an asterisk). Currently there is no recommendations on when at least one item is missing for a participant. Therefore, if this occurs a total score will not be calculated for this participant.

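### One missing item voids the score on the section 6.2 scales of 8 to 28 items, and at baseline the centre mean then replaces nearly complete answers

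*SAP*

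**What the plan says.** Table 16.1 (section 16.1) lists eleven instruments. For nine of them it says "Currently there is no recommendations on when at least one item is missing for a participant" and draws the consequence that "if this occurs a total score will not be calculated for this participant". The other two are the one-item Disclosure Stress Scale and EQ-5D-5L, which is scored from a value set.

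Seven of the nine are section 6.2 outcomes: the Stigma Stress Scale ("An eight-item measure that assesses Cognitive appraisal of stigma as a stressor"), the Calgary scale (CDS, 9 items), SIMS ("A total score is calculated by adding up all 10 items and ranges from 0 to 40"), MANSA (12 items by its formula), QPR (15), SIAS (20) and RES ("28 item questionnaire, scored between 1 (strongly agree) to 4 strongly disagree"). The remaining two, ISS and SERS, are the section 6.3 mediators.

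Section 11.4 models the section 6.2 outcomes, apart from the economic questionnaire, with adjustment for the baseline score. It adds: "For the analysis, missing baseline data will be imputed using the centre-specific mean of that variable". Table 13.2 lists two centres. Section 11.7 plans no formal handling of missing outcome data.

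**The concern.** Each rule can be defended alone; the waste comes from combining them. The scoring rule turns a nearly complete baseline form into a missing variable, and section 11.4 fills that variable with one of two constants, one per centre. The participant's own 27 answers are discarded in favour of a number that says nothing about that person beyond their centre. At follow-up the same skip removes the score for that scale at that visit, and section 11.7 offers no remedy.

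Three things are at stake.
- **Baseline adjustment:** it loses strength, so the confidence intervals widen.
- **Standard deviation for the definitive trial:** fewer scores are available than the 60 sought in section 10. The allowance there covers attrition but does not mention item-level loss.
- **Choice of outcome:** section 6.2 collects these measures to judge their suitability and to identify a primary outcome. An all-or-nothing rule penalises a scale for being long.

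**Working it through.** **Plan's own figure.** Section 10 needs 60 participants with outcome data and allows 20% attrition: 60 / (1 − 0.20) = 75. This reproduces. At exactly 80% follow-up, 75 × 0.80 = 60, with no margin for item-level loss.

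**Inputs.** Item counts m come from Table 16.1. The per-item skip rate q is not in the SAP. It is assumed to be 1%, with 0.5% and 2% as the range, and independent across items.

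**Share of completed forms with no score** = 1 − (1 − q)^m:

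| Scale | m | q = 0.5% | q = 1% | q = 2% |
|---|---|---|---|---|
| Stigma Stress | 8 | 3.9% | 7.7% | 14.9% |
| CDS | 9 | 4.4% | 8.6% | 16.6% |
| SIMS | 10 | 4.9% | 9.6% | 18.3% |
| MANSA | 12 | 5.8% | 11.4% | 21.5% |
| QPR | 15 | 7.2% | 14.0% | 26.1% |
| SIAS | 20 | 9.5% | 18.2% | 33.2% |
| RES | 28 | 13.1% | 24.5% | 43.2% |

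**Baseline.** With 75 participants and q = 1%, 75 × 0.096 ≈ 7 SIMS scores and 75 × 0.245 ≈ 18 RES scores become a centre mean.

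**Follow-up.** With 60 completed measures and q = 1%, 60 × 0.99^10 = 54.3 SIMS totals and 60 × 0.99^28 = 45.3 RES totals remain. For SIMS, the relative standard error of the SD, approximately 1/√(2(n − 1)), rises from 9.2% at n = 60 to 9.7% at n = 54.

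**Clustering of skips within people.** Let the person's skip rate follow a beta-binomial with mean 1%. With within-person correlation 0.1, the loss is 6.8% for SIMS and 12.3% for RES. With correlation 0.2, it is 5.3% and 8.4%. An 80%-answered rule would recover 89% and 77% of the lost SIMS totals at the two correlations, and 93% and 82% of the lost RES totals.

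**How good a prorated score is.** Take exchangeable items, one item missing and Cronbach's alpha of 0.7 to 0.9 (assumed). The inter-item correlation is r = α / (m − α(m − 1)). The correlation of the prorated with the full total is then 0.979 to 0.993 for 8 items, 0.984 to 0.995 for 10 items and 0.995 to 0.998 for 28 items. The 8-item figure treats Stigma Stress as one sum; the actual score is a difference of two subscales, so it is only a guide there.

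**Retention, by reading of section 8**, at an assumed 85% follow-up:

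| What counts as retained | q = 0.5% | q = 1% | q = 2% |
|---|---|---|---|
| Computed SIMS total: 0.85 × (1 − q)^10 | 80.8% | 76.9% | 69.5% |
| A total on either SIMS or Stigma Stress | 84.8% | 84.4% | 82.7% |
| Returned measure, complete or not | 85% | 85% | 85% |

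The green threshold is 80%. Only the first row can cross it, and at q = 0.5% it does not.

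**The case against.** The strongest defence is that the rule is deliberate and its reason is given: no scoring recommendation exists, so the SAP declines to invent one. Nothing in the SAP is contradicted, and no figure in it supports an 80% threshold. This has some force at follow-up. It has little at baseline, because there the SAP does substitute a value, and the substitute is cruder than prorating.

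Several limits on the size also stand. No skip rate is documented, and independence is the unfavourable assumption. SIMS is an interview, so its item loss may be low. A participant with no score at one visit still contributes the other visit to the repeated-measures model. Imputation by centre ignores allocation, so it should not bias the comparison.

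A reader might be tempted to go further in two ways, and the SAP supports neither:

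- **That centre-mean replacement reaches the 30-item scale.** Table 16.1 says of the Internalised Shame Scale "Total score is 30 questions added together", and the one-missing-item rule applies to it. But it is a mediator, which section 11.5 summarises descriptively, and the section 11.4 imputation covers the section 6.2 outcomes. The longest scale affected by both rules is RES.
- **That the rule lowers the retention result, moving it from green to amber.** Section 8 counts data on SIMS or the Stigma Stress Scale and does not say whether a partly completed measure qualifies. The SIMS Total row under response rates in Table 13.1 hints at computed totals but does not settle it. The effect is nil if returned measures count and slight if either measure suffices. Under computed SIMS totals, whether it reaches amber depends on the assumed skip rate.

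**Conclusion.** The point holds for the seven multi-item section 6.2 scales. Tables and text together discard nearly complete answers, most plainly at baseline, where a centre constant takes their place. On the assumed 1% independent skip rate (0.5% to 2%), the loss is about 8% (4% to 15%) of Stigma Stress scores, 10% (5% to 18%) of SIMS and 25% (13% to 43%) of RES, and less with clustering. The consequence is mainly lost precision. For the SD of SIMS it is small; for the longer scales it is larger. A retention effect is possible but conditional on a definition that section 8 leaves open. The change is worth making because it is cheap and is better than the current rule at baseline under mild assumptions, not because the present rule invalidates the trial.

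**What to change.** **Table 16.1**, for summed scales without a published rule (not EQ-5D-5L and not the single-item Disclosure Stress Scale): 'If at least 80% of items are answered, the total is the mean of the answered items, after any reversal, times the number of items; otherwise the score is missing.'

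**Stigma Stress Scale**, separately: 'If at least 3 of the 4 items of each subscale are answered, prorate the harm and coping subscales separately, then subtract coping from harm; otherwise the score is missing.' It needs its own threshold because 80% of four items is 3.2, which would again require all four.

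**Section 11.4:** use the centre mean only when these rules give no baseline score. Show the analysis with the complete-item score as a sensitivity analysis.

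**Reporting:** tabulate item-level missingness by scale as an acceptability result of its own.

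**Section 8 and Table 13.1:** state that retention counts returned measures, so that item skipping is not mixed with drop-out.

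The cost is SAP wording and a few lines of scoring code. The downside is the assumption that a skipped item resembles the person's other answers on that scale. The 80% threshold is a convention to be fixed in advance, and the sensitivity analysis shows whether it matters.
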